Only certain SLE subgroups or organ systems may respond to a particular agent, an important consideration for early phase trials. Concurrent use of immunosuppressive medications, like mycophenolate mofetil, azathioprine, methotrexate and corticosteroids, creates further biologic variability in an already heterogenous disease and confounds the interpretation of data in human studies, since these medications might interfere with or confound the mechanism of the agent(s) studied. This practice also increases the response in the comparator arms, limiting the possible differences between treatment and placebo in SLE clinical trials, necessitating the prolonged study of larger patient numbers for adequate power, and further compromising the clinical interpretability of results. Withdrawal of background immune suppression has been considered as an option to limit study time and patient exposures to untested therapies, but the community has been concerned about its safety. The BOLD (Biomarkers of Lupus Disease) trial, in which a brief course of parenteral steroids is utilized to induce a state of remission or low disease activity while background medications are withdrawn, has shown evidence this approach is safe and effective (11). Time to first flare averaged 72 days (CI 43–91), with 100% of the patients flaring by 24 weeks.

In the BLISS trials of belimumab in SLE the systemic response index (SRI), a composite measure of disease activity, was used as the primary endpoint. SRI is a landmark index defined as the composite of ≥ 4 point reduction in total SLEDAI score, with no new BILAG A or no more than one new BILAG B domain score and no more than 10% worsening in physician's global assessment (PGA), compared to baseline. Another composite measure, the SRI-BILAG (BICLA) has been used in the EMBLEM phase II trial of epratuzumab in SLE. BICLA requires the achievement of BILAG-2004 improvement (BILAG A to B/C/D, BILAG B to C/D, and no BILAG worsening), along with no deterioration in SLEDAI total score and no more than 10% worsening in PGA. In the BOLD study, BICLA was found to be more sensitive to change than SRI, when anchored to the simpler BOLD improvement criteria (drop of \geq one BILAG grade or ≥ 4 SLEDAI points) anchored to the clinician's determination of significant clinical improvement (11).

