Patients will have CBC with differential, metabolic profile, urinalysis, anti-dsDNA, and complement studies performed at baseline, each of the subsequent monthly visits through week 24 and the flare visit. If urine dipstick is $\geq 2+$, a protein/creatinine ratio will be performed at the following visit (or sooner at the discretion of the investigator). Pharmacodynamic and exploratory blood and urine biomarker samples will be drawn prior to first dose at baseline, at weeks 8 or 12, week 24 and at the flare visit. Some of the stimulated cell gene expression and signaling pathway work will be performed on deidentified samples in collaboration with Drs. [name] and [name] at Beth Israel Medical Center in Boston Massachusetts. We will have a material transfer agreement with that institution. In the context of our ancillary study of heart rate variability in lupus, a 5-minute ECG will be performed at each monthly visit and at the flare visit (please see attached protocol).

Summary of Medications and Medication Changes

At screening, participants may be receiving daily prednisone at a dose of 20mg or less, and/or one or more of the following DMARDs: hydroxychloroquine, methotrexate, azathioprine and mycophenolate mofetil, and must be agreeable to discontinue their background immune suppressants upon enrollment. Patients taking hydroxychloroquine upon enrollment will however continue the medication throughout the study.

All participants may be administered optional intramuscular methylprednisolone acetate upon enrollment (usually 160mg, but dose may adjusted based on clinical judgment). Intramuscular steroid treatment may be repeated at weeks 2 at the discretion of the investigator, to induce a state of remission/low disease activity while background medications are withdrawn. Patients on oral steroids will be given an optional rapid taper over 3-4 weeks.

Duration of participation

Participants will receive treatment for a total of 24 weeks.

Patient enrollment

A maximum of 50 patients meeting the inclusion criteria and not meeting the exclusion criteria will be enrolled in the study. The enrollment period is expected to last for at least 18 months but could last as long as four years.

Data collection and analysis

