Data will be collected by study personnel who will be kept blinded to treatment assignments. A trained study coordinator will provide data monitoring and quality assurance checks on the database. The final data will be pooled and analyzed by the investigators.

E. Statistical methods

The primary analysis will be an intention-to-treat two by two table.

Primary endpoint: A two by two table analysis of rate of response by the BICLA response index at week 24 compared to baseline (week 0) in patients on aspirin versus Aggrenox regimens, with non-response attributed to patients who receive defined non-responder treatments and/or withdraw early. Please see below for power calculations based on expected response rates. Independent predictors of BICLA response, including baseline biomarkers, biomarker responses to Aggrenox treatment, demographics and amount of steroids administered, will be further investigated by exploratory logistic regression modeling.

Secondary endpoints: Flare rates at week 24 compared between completers among treatment groups. Time to flare (log rank test). SRI 4/5 at week 24, BICLA and SRI 4/5 at each month. HRQOL comparing treatment groups versus baseline at week 24 and at each month. Although our primary endpoint is based on the BICLA response, an accepted outcome for lupus clinical trials which serves as a pilot response indicator for future trials, it is likely that some secondary endpoints, such as time to flare will be more sensitive, and more likely to achieve significance in a pilot study.

Exploratory endpoints: SRI component analyses and CLASI responses. Refinement in BICLA and SRI analysis using a propensity score derived by multiple potential confounders identified in exploratory single variate analysis. Relation of clinical and biologic endpoints with heart rate variability measures by multivariate analysis.

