Biologic Endpoints: Changes in B cell and T cell subsets, relevant gene expression patterns, B-T cytokine profiles and cell-bound complement split products and urinary biomarkers at baseline versus week 24 in each treatment group. Evaluation of B Cell/T cell expression patterns in patients with higher versus lower IL6, IL17 and IL23 expression detected at baseline. These endpoints will be evaluated both as changes with Aggrenox versus aspirin treatment (non parametric analysis) and as components of multivariate modeling and propensity score analysis as described above. An exploratory responder analysis will also be performed (changes in these biomarkers with response versus non-response in patients receiving Aggrenox). The latter analysis may need to be observational only, as it is likely to be underpowered and diluted by patients who may not have begun the trial with the characteristic abnormalities in T cell subset activity.

Power/Sample size calculation

We base this calculation on preliminary data from the BOLD study (11) which is an exploration of underlying biology in patients with SLE who receive steroids and are withdrawn from background treatments, in other words identical to the aspirin group in the current proposal. To date we have analyzed data from 31 patients who completed the BOLD protocol and these outcomes suggest that no more than 20% of the aspirin group will achieve a BICLA response at week 16 (range 1-20%) and no more than 5% achieves a BICLA response at week 24 (range 0-10%). Assuming a 35 to 50% response rate in the Aggrenox group at week 24, a sample size of 50 patients will provide a power around 80% at a significance level of 0.05 at week 24. By these settings and assumptions, the following power estimates are obtained.

Power calculations for a 50 patient study, if alpha=0.05 with response rates:

	Rate 1	Rate 2	Rate 3	Rate 4	Rate 5	Rate 6	Rate 7
Aggrenox n=25	60%	55%	50%	45%	40%	35%	35%
Aspirin n=25	20%	15%	10%	10%	5%	5%	3%
power	0.84	0.86	0.89	0.80	0.86	0.77	0.84

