An absolute difference of ≥ 12 to 15% in the response rate is however considered clinically significant in other lupus trials. Since this is a pilot study, a clinically significant (12% or greater absolute difference), but not statistically significant difference, might be considered justification for a larger study. Even if this pilot study does not reach statistical significance, the proposed exploratory biomarker studies evaluating T and B cell phenotypes, T/B cell functional studies, gene expression or serum cytokine/chemokine profiles might be used to refine the entry criteria and biologic treatment goals for a further study and/or underscore the rationale for an expansion of this study for more power of discrimination. Finally, the BICLA and other flare analyses will be performed at each monthly visit, increasing the likelihood of finding differences, should they exist, when including these secondary analyses.

An interim analysis will be performed after 20 patients will have completed the study, and will be used to assess the quality of the data collected and the treatment effects. Consideration of sample size changes can be discussed at that time.

F. Gender/Minority/Pediatric Inclusion for Research

Participants will be age 18 or older. Race, minority status and gender will not affect enrollment.

G. Human participants

The study population will include male/female patients with SLE, of age 18 or older and of all races.

Inclusion Criteria:

1. Patients with SLE meeting the ACR Classification Criteria (19)
2. Males or females, age 18-70
3. Evidence of positive ANA or anti-dsDNA within one year of screening
4. SLEDAI ≥ 4 or ≥ 1 BILAG B or A at screening, despite standard of care

Exclusion Criteria

1. WBC $< 2,000/\text{mm}^3$, lymphocytes $< 300/\text{mm}^3$ (last known labs)
2. AST or ALT > 3 times above normal cut off values (last known labs)
3. Acute lupus nephritis defined as class II, III, IV or V nephritis diagnosed within 6 months or prot/creat > 1.5 gm/gm due to active lupus or in process of receiving induction therapy for nephritis
4. Active CNS lupus affecting mental status
5. Pregnancy or breast feeding
6. Current requirement for anticoagulation
7. Contraindication to aspirin or dipyridamole, including history of recent or severe GI bleeding, hemoglobin < 9 mg/dL, platelet count of $< 30,000/\text{mm}^3$ or unstable platelet count (last known labs)

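### Entry on SLEDAI alone can admit patients with no BILAG A or B at week 0, who cannot meet the primary BICLA endpoint as defined but still count in its two-by-two table; the size of the dilution is unknown

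*Combined protocol and SAP*

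**What the plan says.** **Entry.** Section G, Inclusion Criteria, item 4: "SLEDAI ≥ 4 or ≥ 1 BILAG B or A at screening, despite standard of care". The two scales are alternatives and are judged at screening. No other section asks for a BILAG A or B at week 0.

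**Endpoint.** Section C gives the only component-level definition: "BICLA requires the achievement of BILAG-2004 improvement (BILAG A to B/C/D, BILAG B to C/D, and no BILAG worsening". It adds conditions on SLEDAI and the physician's global assessment. The primary objective in section A also describes the endpoint as improvement from baseline.

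**Analysis.** Section E: "The primary analysis will be an intention-to-treat two by two table", of the "rate of response by the BICLA response index at week 24 compared to baseline (week 0". Non-response is assigned for defined nonresponder treatments and for early withdrawal. Patients with no A or B at baseline are not mentioned.

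**Secondary SRI.** Section C: "SRI is a landmark index defined as the composite of ≥ 4 point reduction in total SLEDAI score".

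**Use of the result.** Beyond the significance test, section E says that "a clinically significant (12% or greater absolute difference), but not statistically significant difference, might be considered justification for a larger study".

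**Status.** The January 2015 amendment interrupts the randomised part (group A) temporarily. Group B uses the same entry criteria but has no control arm, so this point concerns group A only.

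**The concern.** The entry rule and the endpoint do not match. A patient can qualify through SLEDAI, have no BILAG domain at A or B at week 0, and so have nothing that the BICLA definition lets improve. That patient adds one to the denominator and nothing to the numerator, whichever arm is assigned.

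The cost is sensitivity. Such patients shrink the absolute difference, which drives both the significance test and the 12-point signal for a larger study. With 25 per arm and power described as around 80%, there is little slack.

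The SRI endpoint has the mirror-image gap. A patient admitted on BILAG alone with baseline SLEDAI below 4 cannot fall by 4 points.

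**Working it through.** **Inputs from section E:** 25 per arm, alpha 0.05, and seven pairs of response rates with stated power 0.84, 0.86, 0.89, 0.80, 0.86, 0.77 and 0.84. **Assumed:** f, the share with no A or B at week 0, taken as 10% or 20% and equal in both arms in expectation because it is fixed before treatment.

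**1. The plan's own figures.** Two-sided pooled normal approximation:

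power = Φ[(|p1−p2| − 1.96·s0)/s1], with s0 = √(2p̄(1−p̄)/n) and s1 = √((p1(1−p1)+p2(1−p2))/n).

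For 35% vs 5%: p̄ = 0.20, s0 = 0.1131, s1 = 0.1049, so Φ[(0.30 − 0.2217)/0.1049] = Φ(0.746) = 0.772 (stated 0.77). All seven columns reproduce to within about one point.

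**2. Dilution, if the planned rates describe patients able to respond.** Both rates are multiplied by (1−f). For 35% vs 5% at f = 10% the rates become 31.5% vs 4.5%: s0 = 0.1087, s1 = 0.1017, and Φ[(0.27 − 0.2130)/0.1017] = Φ(0.560) = 0.712.

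| Aggrenox vs aspirin | f = 0 | f = 10% | f = 20% |
|---|---|---|---|
| 60 vs 20 | 0.845 | 0.772 | 0.690 |
| 55 vs 15 | 0.866 | 0.801 | 0.725 |
| 50 vs 10 | 0.895 | 0.839 | 0.771 |
| 45 vs 10 | 0.811 | 0.747 | 0.676 |
| 40 vs 5 | 0.865 | 0.811 | 0.746 |
| 35 vs 5 | 0.772 | 0.712 | 0.646 |
| 35 vs 3 | 0.844 | 0.790 | 0.726 |

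**3. If the planned rates already include such patients.** The stated power stands. Matched entry, with excluded patients replaced, raises the rates to p/(1−f). At 35% vs 5%, power goes from 0.772 to 0.830 (f = 10%) or 0.889 (f = 20%).

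**4. The 12-point signal.** With 25 per arm, 12 points is 3 patients (0.12 × 25). Exact binomial probability of a difference of at least 3:

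| True rates among patients able to respond | f = 0 | f = 10% | f = 20% |
|---|---|---|---|
| 35 vs 5 (planned) | 0.974 | 0.956 | 0.927 |
| 20 vs 5 (assumed; below the planned range) | 0.706 | 0.650 | 0.586 |

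**5. What a supportive table recovers.** Restricting to patients with a week-0 A or B gives n = 25(1−f) per arm at undiluted rates. At 35% vs 5% by pooled z, power is 0.726 against 0.712 (f = 10%) and 0.672 against 0.646 (f = 20%). Over f from 5% to 30% the gain is about 1 to 4 points. By Fisher's exact test it is roughly 1 to 9 points, but the figure depends on rounding. At f = 5%, keeping everyone gives 0.668, while the subset gives 0.706 with n = 24 and 0.679 with n = 23. Section E does not name the test.

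**The case against.** **No effect is demonstrated.** The share f appears nowhere, and section D says that patients enter with active disease. That does not guarantee an A or B, but nothing points to a large f. This stands: every loss above is conditional on an assumed f.

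**The planning rates may already allow for it.** Section E describes BOLD patients as "identical to the aspirin group in the current proposal". If BOLD admitted similar patients, the aspirin rate includes them, and the Aggrenox rate is simply assumed. BOLD's entry criteria are not given, so this cannot be settled. A reader might infer that the power table is wrong or the trial underpowered; the documents do not support that.

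**The BICLA wording is a background summary.** A rule that all baseline A or B scores must improve could be read as vacuously met when there are none. The protocol's insistence on achieved improvement weighs against this. On that reading the dilution figures would not apply, but a stable patient would be a responder without improving. Either way these patients carry no information on BILAG improvement, and the scoring rule is unstated.

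**Broad entry suits a pilot.** Patients without an A or B still inform time to flare, which section E expects to be more sensitive, and the biomarker aims. This is a fair reason to keep them in the all-randomised table.

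**Conclusion.** The mismatch stands: as written, the plan can count in its primary table patients who cannot meet the endpoint. It rests on reading section C's definition as requiring an actual improvement from A or B. The consequence is a possible loss of sensitivity of unknown size: about 5 to 7 points of power per column at f = 10% if the planned rates describe patients able to respond, and none if f is zero or the rates already include such patients.

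Three stronger readings go too far:

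- **That everyone admitted on SLEDAI alone is a lost patient.** Someone with an A or B by week 0 can still respond.
- **That the 12-point signal is in serious danger.** At the planned 35% vs 5% the chance of seeing it stays at 0.93 or above for f up to 20%. The larger loss arises only if the true effect is smaller than planned.
- **That the comparison is biased or type I error inflated.** The feature precedes treatment and is balanced in expectation; with equal f the rate ratio is unchanged.

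This is a cheap improvement to the design and analysis, not a demonstrated error in the sample size.

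**What to change.** **If group A resumes:** require at least one BILAG A or B at week 0. BILAG is already scored at that visit, so no new assessment is needed.

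**For patients already randomised:**

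- Keep the all-randomised table as primary, state that patients without a week-0 A or B are scored as nonresponders, and report their number by arm.
- Before unblinding, pre-specify a supportive two-by-two table in patients with a week-0 A or B, and read the 12-point signal in both tables.
- Add supportive SRI-4 results in patients with baseline SLEDAI of at least 4.

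**Cost:** one edited criterion and a few sentences of analysis text. The population becomes narrower. Filling the maximum of 50 needs 50/(1−f) otherwise eligible candidates: about 56 at f = 10% and 63 at f = 20%, from one clinic. Entry criteria would differ before and after the change, and the share with baseline SLEDAI below 4 may rise, widening the SRI gap. The edit helps only patients still to be enrolled. If half of group A were already in (an assumption; the number is not given), power at 35% vs 5% under the first reading would return only to 0.743 (f = 10%) or 0.712 (f = 20%). If group A does not resume, the edit does nothing and only the analysis changes apply.

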We will modify the DARE protocol as following: The randomized controlled part of the study (group A) will be temporarily interrupted in order to focus our work on the pharmacology of Aggrenox. Patients enrolled will be assigned to open label Aggrenox for 3 months (group B) using the same protocol as in the randomized controlled study. There will be no control arm in this modified phase. We plan to enroll in group B 10 more patients with mild to moderate disease, using the same inclusion and exclusion criteria as in the parent study (group A). However, only patients with a Th17 signature, defined by serum cytokine and gene expression profiling, will be invited to participate in group B. Patients will be instructed to hold their background medications as in the parent study, and will not be allowed to receive any additional steroids. Patients who flare during this study or who have persistently active disease, may elect to be treated with steroids and other immune suppressants as needed, but will be nonresponders for the primary endpoint at 3 months.
